### 10.3 Enrolment and Assignment and Trial Number

The patient will be allocated a unique trial identification number to be used on all trial related material for the patient upon enrolment. Patients will be enrolled by logging into an internet based website (TENALEA) provided by the Cambridge Clinical Trials Unit. After logging in, the investigator will confirm eligibility criteria, ANCA subtype, relapse severity and the prednisolone induction regimen followed (1A or 1B). Investigators are required to enter the height and weight of the patient. Body surface area and the dose for each of the 4 rituximab induction infusions ( $375\text{mg}/\text{m}^2$ ) will be automatically calculated within TENALEA using the Dubois and Dubois formula (17). A target date for randomisation four months in the future will be generated. This information should be recorded on the enrolment CRF page.

## 10.4 Randomisation

At the time of enrolment, a target date for randomisation (4 months from enrolment) will be generated. Randomization will be performed by the local investigator **for those patients in remission (BVAS/WG  $\leq$  1 and daily prednisone dose  $\leq$  10mg) by month 4.**

Patients can be randomised from 14 days before, to 14 days after, month 4. If patients attend their month 3 visit and are in remission, then they can be randomised up to 14 days before month 4, to enable time to organise rituximab infusion or azathioprine supply according to treatment allocation. Those not in remission at month 3 are reassessed at month 4 and if they enter remission must be randomised and commence allocated therapy within the next 14 days. Those not in remission at month 4 are not randomised, even if they had been considered in remission at the month 3 visit, and are treated at the investigator's discretion. Follow-up data will continue to be collected unless consent is withdrawn.

The randomization algorithm will then assign the patient to either the rituximab maintenance therapy or the control arm, where patients receive azathioprine, unless there is a contraindication when mycophenolate mofetil or methotrexate are alternatives (see section 11.1.4). **Maintenance therapy with rituximab or azathioprine must not be administered prior to the month 4 visit.** Notification of the treatment allocation will be forwarded to the central study co-ordinator, local investigator and local pharmacy by electronic mail (email) upon randomization. In the event that access to the internet is unavailable, the investigator may call the central study coordinator, based at Addenbrooke's Hospital, Cambridge, UK who will access the randomization program and inform the investigator of the treatment allocation and ensure randomization information reaches the appropriate study personnel.

Patients will be stratified at the time of randomisation according to:

1. ANCA type (anti-PR3 or anti-MPO)
2. Relapse severity (severe or non-severe)
3. Selected prednisone induction regimen (1A or 1B)

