### 9.6 Trial Endpoints

#### 9.6.1 Primary endpoint

The primary endpoint is the time to disease relapse (either minor or major relapse) from randomisation. Any patients who have not relapsed at study close will be censored. Further details of how relapse/censoring dates will be defined are given below.

A blinded Independent Adjudication Committee will be convened to look at all endpoint data.

Situation	Date of Relapse or Censoring	Outcome
No baseline assessments	Randomization	Censored
Relapse documented between scheduled visits	Unscheduled visit date	Relapsed
Drop-out with no relapse	Date of last assessment with no documented relapse	Censored
Treatment discontinuation for undocumented relapse	Date of last assessment with no documented relapse	Censored
Treatment discontinuation for toxicity or other reason, or protocol deviation	The patient will be followed up as per protocol and date of relapse or censoring observed accordingly	Relapsed/censored
Death due to relapse	Date of Death	Relapsed
Death due to other causes	Date of Death	Censored
Death or progression after More than one missed visit	Date of last assessment with no documented relapse	Censored

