## 10.5 Method of Blinding

This will be an open label study.

A non-blinded, open label study has been chosen for *reasons of simplicity and practicality* in view of RITAZAREM being an international multi-centre trial. Previous EUVAS studies with similar end-points have also been unblinded yet have led to robust and reproducible conclusions.

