#### 5.2.1 Primary endpoint

The primary endpoint is the time to disease relapse (either minor or major relapse) from randomisation. Any patients who have not relapsed at study close will be censored. Further details of how relapse/censoring dates will be defined are given below (Table 1).

In the efficacy analysis, the date of the month 4 visit will be used as time-zero (i.e. randomisation). According to the protocol, patients might be randomised in advance of the month 4 visit (provided they achieved disease remission by the month 3 visit), however maintenance therapy (with either treatment) was not allowed to be administered before the month 4 visit.

---

 For a more in-depth description of randomisation procedures and trial's timelines, including definitions of the induction and maintenance phase, see Induction Phase SAP, section 9.1.1, and refer to the protocol, section 10.4.

Treatment duration is taken to be strictly 20 months post-randomisation, i.e. date of the month 4 visit + 20 months, and not the actual time of the month 24 visit when the last visit was administered. This affords a common timeline for all patients, irrespective of time slippages in the schedule of visits.

In the analysis, the censoring rules detailed in Table 1 will be implemented. Censoring time will be taken from the last assessment with no documented relapse (scheduled visit), the date of death (unscheduled visit) or the common close date. The time of relapse will be taken from the relapse form (unscheduled visit). Further particulars are detailed in section 10.3.

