### 8.2.2 Full Analysis Population (randomised patients)

The full analysis population is defined as all participants who achieved remission in the induction phase of the trial and were randomised to the maintenance phase, regardless of whether they actually received any maintenance treatment. The treatment group will be analysed as randomised (rituximab or azathioprine).

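### The SAP starts the clock at the month 4 visit, so a relapse after early randomisation goes uncounted, and no rule covers an already allocated patient who fails the month 4 remission check

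*Protocol*

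**What the plan says.** **Entry.** Protocol 10.4 provides: "If patients attend their month 3 visit and are in remission, then they can be randomised up to 14 days before month 4". The purpose given is to leave time to arrange supply for the allocated arm. On disclosure it says: "Notification of the treatment allocation will be forwarded to the central study co-ordinator, local investigator and local pharmacy by electronic mail (email) upon randomization". Protocol 10.5 adds: "This will be an open label study". The paragraph that opens the early window also says: "Those not in remission at month 4 are not randomised, even if they had been considered in remission at the month 3 visit". SAP 9.1.1 repeats both rules. Neither arm may start maintenance drug before the month 4 visit.

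**Time origin.** Protocol 9.6.1: "The primary endpoint is the time to disease relapse (either minor or major relapse) from randomisation". SAP 5.2.1, with the same effect in 9.1.1 and 10.3, says that "the date of the month 4 visit will be used as time-zero (i.e. randomisation"). SAP 10.1 reports events after randomisation and equates this with leaving out the induction phase. SAP 9.1.1 runs that phase up to and including month 4.

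**Population.** SAP 8.2.2 defines the full analysis population as "all participants who achieved remission in the induction phase of the trial and were randomised to the maintenance phase", whether or not maintenance treatment was received. SAP 8.2 has the trial management team agree membership of each population before the analysis.

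**The concern.** For most patients, randomisation and the month 4 visit nearly coincide and the wording does no harm. For a patient randomised early on the month 3 check, they are up to 14 days apart, and two things follow.

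First, the primary endpoint loses part of its own follow-up. The protocol defines relapse as any new BVAS/WG item. A patient in remission at month 3, allocated at day -10, who shows a new item before or at month 4 has relapsed after randomisation. Under the SAP that relapse belongs to the induction phase, and when it precedes the visit it also precedes time-zero. No rule in SAP 10.3 brings it back.

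Second, the month 4 remission check is made by an investigator who already knows the arm, and Protocol 10.4 describes anyone who fails it as not randomised. If such patients were left out of the analysis, the omissions could differ by arm. In an open-label trial that is a worse problem than the loss of a few events.

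**Working it through.** **1. The plan's own figure.** Protocol 16.3 gives 58 relapses for 90% power at a hazard ratio of 0.42, 5% level; SAP 10.1 makes the test two-sided. With 1:1 allocation, Schoenfeld's formula gives 4 × (1.960 + 1.282)² / (ln 0.42)² = 56 events, and 58 events give power 0.910. The figure reproduces, so 58 is a fair yardstick.

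**2. Length of the gap.** At most 14 days. With the SAP 9.1.1 month of 365.25/12 = 30.44 days, this is 14/30.44 = 0.460 months.

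**3. Hazards**, taken as constant (an assumption).
- Control planning rate, 50% relapse-free at 4 years: ln 2 / 48 = 0.01444 per month.
- Rituximab planning rate, 75% at 4 years: -ln 0.75 / 48 = 0.00599 per month.
- Pilot patients without scheduled re-treatment, 71% relapsed at 24 months (caption to protocol Figure 1): -ln 0.29 / 24 = 0.0516 per month.

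**4. Relapses in the gap**, N × (1 - exp(-hazard × 0.460)).

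| Hazard in the gap | Probability | All 160 early | A quarter (40) early |
|---|---|---|---|
| Control, both arms | 0.66% | 1.06 | 0.26 |
| Arm-specific | 0.66% and 0.28% | 0.75 | 0.19 |
| Pilot 71% | 2.34% | 3.75 | 0.94 |

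No maintenance drug is given in the gap, so the control hazard suits both arms. Against 58 events, 1.06 is 1.8% and 3.75 is 6.5%. Using the 77% relapse within 2 years from Protocol 8 instead gives 4.4 relapses.

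**5. If patients were also dropped** (a what-if; the documents do not direct it).
- Evenly across arms, events scale as 58 × (160 - k)/160. Dropping 4, 8 or 16 patients gives power 0.904, 0.896 or 0.880.
- From the rituximab arm only, removing k patients who would have relapsed, with 80 per arm and 60 against 40 relapse-free, the hazard ratio is ln(60/(80 - k)) / ln 0.5. It moves from 0.415 at k = 0 to 0.397, 0.379 and 0.341 at k = 1, 2 and 4.

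Even loss hardly matters. One-sided loss of very few patients would.

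**6. Would an early-randomised patient who fails at month 4 stay in the analysis?**
- For: Protocol 16.1 and SAP 8.9 specify intention to treat. SAP 8.2.2 does not require treatment to have been received. The note to the CONSORT diagram in SAP 9.1.3 keeps all randomised patients, including later withdrawals.
- Against: Protocol 10.4 labels the patient not randomised. SAP 8.2.1 has a separate induction group for enrolled but unrandomised patients. SAP 8.2.2 adds a remission condition, and SAP 8.2 leaves membership to agreement.
- No sentence names this patient.

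**The case against.** A reader might infer that the plan permits patients to be excluded after allocation. The documents do not support that. Besides the intention-to-treat wording, an early-randomised patient was in remission at month 3, which lies inside the induction phase, and so meets the remission condition of SAP 8.2.2 as written. Table 3 in SAP 9.1.2 files failure at month 4 under withdrawal from protocolised treatment, not from the study, and Protocol 10.4 continues data collection. The month 4 sentence can also be read as addressing only patients who were in remission at month 3 but had not been randomised early. All of this stands. What remains is that the allocated patient is not mentioned and the label in 10.4 points the other way.

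A reader might also infer that sites would use the month 4 score to steer patients. Nothing in the documents shows this. Protocol 10.6 requires any stop of randomised treatment to be discussed with the chief investigator, and relapses go to blinded adjudication. That adjudication is not, however, stated to cover the month 4 remission decision.

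The time origin is disclosed and reasoned: with no maintenance drug before month 4, no treatment effect is expected in the gap, and events there dilute the hazard ratio. That is a good argument for a sensitivity analysis. It does not make the month 4 visit the protocol's endpoint, which starts when allocation is fixed.

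The size is also easy to overstate. Only patients in remission at month 3 can be early, and few will be early by the full 14 days. The pilot rate spreads a two-year risk evenly, although Protocol 11.1 says B cells typically begin to return only after four months.

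**Conclusion.** The point holds in a limited form. For early-randomised patients, the SAP's time-zero and event count depart from the protocol's endpoint, and a relapse between allocation and the month 4 visit is not counted as a primary event. Separately, Protocol 10.4 and SAP 8.2.2 do not state what happens in the analysis to an allocated patient who fails the month 4 check. This is an unreconciled gap, not a licence to exclude.

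The numerical effect is small: about 1 relapse of 58 if all 160 were 14 days early at the planned control hazard, 0.2 to 0.3 at the planning hazards if a quarter were, and about 4 only as an upper bound under the pilot hazard. These figures rest on constant hazards and on an early-randomised share that the documents do not give. The change is worth making before database lock because it closes a route to arm-related loss in an open-label primary analysis.

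**What to change.** 1. **SAP 8.2.2:** state that every patient to whom an allocation was released is in the full analysis population, regardless of the month 4 BVAS/WG.
2. **SAP 5.2.1, 9.1.1, 10.1 and 10.3:** time the primary analysis from the actual randomisation date, and count a relapse between randomisation and the month 4 visit as an event on its date. The date named in SAP 9.1.1 (*RandomDate*) is a target set at enrolment and will not serve; the web-based randomisation system should hold the real one. State also whether the 20-month boundary in SAP 10.1 stays anchored on the month 4 visit.
3. **Sensitivity analysis:** keep the month 4 visit as an alternative origin.
4. **Reporting:** give, by arm, the number randomised before month 4 and how many of them were not in remission at month 4.
5. **Protocol 10.4 and SAP 9.1.1:** the sponsor must reconcile the early-randomisation and month 4 sentences for a patient already allocated. How such patients are treated is not for this review.

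The cost is SAP wording, one sensitivity analysis and a small table. The downside is that a few events will fall before maintenance drug starts, which slightly dilutes the hazard ratio.

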## 10.5 Method of Blinding

This will be an open label study.

A non-blinded, open label study has been chosen for *reasons of simplicity and practicality* in view of RITAZAREM being an international multi-centre trial. Previous EUVAS studies with similar end-points have also been unblinded yet have led to robust and reproducible conclusions.

## 10.6 Subject Withdrawal Criteria

Patients will be withdrawn from the trial immediately if they choose to withdraw their consent to participate. Otherwise subjects will be followed until the end of the trial or until death. In the event that consent to participate is withdrawn, it will be requested of patients that the study team continue to be allowed to collect vital status information from the patient and/or their family physician or general practitioner. Subjects who are withdrawn will not be replaced. Subjects will not be randomized if they do not achieve disease control (BVAS/WG  $\leq$  1 and daily prednisone dose  $\leq$  10mg) by month 4 and will

be treated at the discretion of the local investigators, although they will continue to be followed and data collected for safety purposes.

**Withdrawal is anticipated to be a rare occurrence.** Local investigators may stop the randomised treatment for appropriate medical reasons, be that individual adverse events or new information gained about a treatment. Pregnant patients will be treated with best medical practice, and continue in long term follow up. Non-compliant patients will be helped to return to protocol compliance, and continue in long term follow up. Any decision to stop the randomised treatment **MUST** be discussed with the chief investigator in order not to adversely affect the conduct of the trial. Patients will continue to be followed up, and data collected and documented as set out in the protocol, unless they withdraw their consent for this.

## 11 Trial Treatments

Rituximab, azathioprine, methotrexate and mycophenolate mofetil are all considered IMPs for the purposes of this study. Glucocorticoids are a non-IMP.

### 11.1 Rituximab

*Rationale for rituximab dosing*

#### Induction Phase:

375mg/m^2/week x 4 doses, was the dose used in both the randomised controlled rituximab induction trials in vasculitis (RITUXVAS and RAVE) and will be the induction dose used in RITAZAREM.

#### Maintenance Phase:

Neither RITUXVAS nor RAVE addressed the question of repeat dosing with rituximab as a maintenance strategy. The two largest data sets presently available utilising repeat rituximab as a maintenance strategy, employed doses of 1000mg x 2 every 6 months (Mayo Clinic) (total 8000mg in 24 months) or 1000mg every 6 months (Cambridge, UK) (total 4000mg in 24 months). The selected dose for RITAZAREM, 1000mg every 4 months (5000mg in total), falls between these two regimens. In addition, 9 out of 10 relapses seen in the Cambridge cohort occurred in the 2 months prior to a scheduled rituximab dose, yet responded to further rituximab. Reducing the interval between rituximab doses to 4 months has the potential to further reduce relapse rates.

B cell depletion is a pharmacodynamic surrogate for rituximab efficacy. Because B cell return typically commences after four months, by reducing the dosing interval to four months the study aims to maintain 100% B cell depletion for the 24 month treatment phase.

No data exists for a total rituximab dose below 1000mg in vasculitis. Adopting a 375mg/m^2 dose every 4 months as a maintenance strategy would result in a median dose of 700mg. The MAINRITSAN study is employing a 500mg dose every 6 months. This is likely to result in under dosing, because 20% of patients relapsed using 1000mg every 6 months in the Cambridge cohort. In addition, more frequent maintenance dosing is inconvenient for patients and more expensive.

#### 11.1.1 Dosage schedules

##### Induction Regimen

Patients will be recruited at the time of relapse. All will receive rituximab 375 mg/m^2/week x 4 doses and glucocorticoids. The first dose of rituximab

should be given within 14 days of enrolment into the trial. All induction doses of rituximab should be completed by week 6.

Patients that achieve disease control (BVAS/WG  $\leq 1$  and daily prednisone dose  $\leq 10$ mg) by month 4 will be randomised to the rituximab or control remission maintenance groups.

First infusion: The recommended initial infusion rate for rituximab (MabThera/Rituxan) is 50 mg/h; subsequently, the rate can be escalated in 50 mg/h increments every 30 minutes to a maximum of 400 mg/h.

Subsequent infusions: Subsequent infusions of rituximab (MabThera/Rituxan) can be started at a rate of 100 mg/h and increased by 100 mg/h increments every 30 minutes to a maximum of 400 mg/h.

Pre-medication with 100 mg IV methylprednisolone will be administered prior the first infusion to minimise infusion reactions. Sites will follow local pre-medication practice for infusions 2, 3, and 4. 100 mg IV methylprednisolone will be administered prior to *each* maintenance dose.

Infusions of rituximab in the maintenance phase should be given within 2 weeks of the randomisation at month 4 (if randomisation allocation is to the rituximab arm). Further infusions at month 8 onwards must be given within +/- 2 weeks of the assessment date.

#### Rituximab maintenance group

Rituximab 1000 mg x 1 dose at months 4, 8, 12, 16 and 20 and glucocorticoids.

**Dose of rituximab for maintenance therapy must not be administered prior to the month 4 visit.**

#### 11.1.2 Route of Administration

Rituximab will be administered intravenously.

#### 11.1.3 Maximum dosage allowed

The induction dose will vary depending on the body surface area of the patient. The maximum dose administered during the maintenance phase will be 5g.

#### 11.1.4 Maximum duration of treatment of a subject

Treatment with rituximab will cease at month 20. Patients will continue to be followed until month 36 at a minimum.

#### 11.1.5 Known Drug Reactions & Interaction with Other Therapies

Infusion reactions (within 24 hours of the infusion) occur in up to 50% of patients receiving rituximab. Pre-medication with 100 mg IV methylprednisolone will be administered prior the first infusion to minimise the effect of such reactions. Administration of 100 mg IV methylprednisolone for induction infusions 2, 3, and 4 is at the local investigator's discretion. 100 mg IV methylprednisolone will be administered prior to *each* maintenance dose. Symptoms include – fever, rigors, urticaria/rash, pruritis, flushing, angiodema, nausea, vomiting, fatigue, headache, rhinitis, throat irritation, bronchospasm and hypotension. Following treatment, sepsis, leucopaenia and neutropaenia can occur. In patients with autoimmune diseases, severe skin reactions such as Toxic Epidermal Necrolysis (TEN) and Stevens- Johnson Syndrome (SJS) with

fatal outcome have been reported very rarely with Rituximab in the post-marketing setting. For autoimmune and oncology indications, in case of the occurrence of severe skin reactions, Rituximab treatment should be discontinued. The decision to re-administer Rituximab must be carefully assessed based on the individual patient's benefit-risk profile. The cases of TEN and SJS have been reported with either first time use or with later infusions. Some of the cases occurred on the day of dosing or within a few days of dosing. In other cases, the event occurred weeks or up to four months after the dose.

Please always refer to the Investigator Brochure for expected adverse events associated with rituximab administration.

#### 11.1.6 Dosage Modifications

Rituximab will be administered at a dose of  $375\text{mg}/\text{m}^2 \times 4$ , at weekly intervals during the induction phase of the trial. Patients achieving remission and randomised to the rituximab remission maintenance group will receive rituximab 1000mg, at months 4, 8, 12, 16 and 20. The dose of rituximab does not need to be adjusted for renal function.

If the IgG level falls below 3g/l, it should be repeated in the month prior to the next scheduled dose of rituximab and the dose not administered if the IgG level remains  $<3\text{g}/\text{l}$ . If the IgG level has risen and is  $\geq 3\text{g}/\text{l}$ , then rituximab should be administered as per protocol. For those with an IgG level remaining  $< 3\text{g}/\text{l}$ , the IgG level is checked again within the month prior to the next scheduled dose of rituximab and this dose only given if the level has risen to  $\geq 3\text{g}/\text{l}$ . IgM and IgA levels are ignored for the purpose of rituximab dosing. Dosing of azathioprine (methotrexate and mycophenolate mofetil) should continue according to protocol regardless of IgG level.

